6.2.3 Lactate at 72-hours

Assuming no unbalanced potentially confounding variables (as would be expected in this randomized trial), we will compare repeated measures of lactate levels at each time point (0h, 24h, 48h, 72h) between arms using repeated measures analysis. A compound symmetry covariance structure will be used. If a patient receives renal replacement therapy or dies before any time point, lactate levels will be imputed by carrying forward the last known value before the event.

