2.2 Allocation

Participants will be randomized in a 1:1 ratio to either thiamine or placebo in blocks with random sizes of 2 or 4. The randomization will be stratified according to site.³⁸ An independent statistician will create the randomization list using a random number generator. The complete list will only be shared with an independent pharmacy consultant, who will not be involved in clinical care. The pharmacy consultant and the independent statistician will both store the randomization list.

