6.2 Statistical analysis plan

6.2.1 General considerations

The statistical analyses and reporting will adhere to the CONSORT guidelines.^{42,43} All tests will be two-sided, a p-value < 0.05 will be considered significant, and all confidence intervals will have 95% coverage. All analyses will be conducted on a modified intention-to-treat basis only including participants receiving at least the first dose of the study medications. In a double-blind trial, this approach is unbiased while increasing precision.⁴⁴ The two groups will be compared in relation to baseline characteristics using descriptive statistics.

The persons conducting the statistical analysis will be blinded to the randomized allocation. Groups will be designated as “A” and “B” until all pre-specified analyses are performed and shared with all authors and the Data Safety Monitoring Board.

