6.2.2 Creatinine at 72-hours

Assuming no unbalanced potentially confounding variables (as would be expected in this randomized trial), we will compare repeated measures of creatinine levels at each time point (0h, 24h, 48h, 72h) between arms using repeated measures analysis. A compound symmetry covariance structure will be used. If a patient receives renal replacement therapy or dies before any time point, creatinine levels will be imputed by carrying forward the last known value before the event. Study site will be controlled for as a fixed-effect in the regression model.

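### The lactate model states no site term, although randomisation is stratified by site and the near-identical creatinine model adjusts for it (minor)

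*Protocol*

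**What the plan says.** Section 2.2 of the protocol has participants "randomized in a 1:1 ratio to either thiamine or placebo in blocks with random sizes of 2 or 4", and adds: "The randomization will be stratified according to site". The Trial Overview names three sites.

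Section 6.2.2 (creatinine) specifies a repeated measures analysis at 0, 24, 48 and 72 hours, compound symmetry, and carry-forward after renal replacement therapy or death. It ends: "Study site will be controlled for as a fixed-effect in the regression model".

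Section 6.2.3 (lactate) says "we will compare repeated measures of lactate levels at each time point", that is at 0, 24, 48 and 72 hours, with the arms contrasted in a repeated measures analysis. It then gives the covariance structure, "A compound symmetry covariance structure will be used", and the rule after renal replacement therapy or death: "lactate levels will be imputed by carrying forward the last known value before the event". It stops there, without mentioning site.

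Section 6.2.1 sets the level for every analysis, "All tests will be two-sided, a p-value < 0.05 will be considered significant", but has no general rule on adjusting for site.

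**The concern.** The two models follow one template for the same patients and time points, and the site sentence is the only substantive difference between them. No reason is given for dropping it.

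Stratified blocks keep the arms nearly balanced within each site, so differences between sites contribute almost nothing to the difference between arms. A model without site still counts those differences as residual variation. Its standard error is then larger than the design warrants, and some of the benefit of stratifying is given up. Section 4.5.2 has each site's own clinical laboratory measure lactate, and 4.6 leaves sepsis care to local guidelines. Some difference in level between sites is therefore plausible, though the protocol does not quantify one.

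The silence also leaves two defensible lactate models, with and without site. That choice is better made before the data are seen.

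**Working it through.** **Comparison of the text**

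| Element | Creatinine, 6.2.2 | Lactate, 6.2.3 |
|---|---|---|
| Time points | 0, 24, 48, 72 h | 0, 24, 48, 72 h |
| Method | repeated measures | repeated measures |
| Covariance | compound symmetry | compound symmetry |
| After renal replacement therapy or death | last value carried forward | last value carried forward |
| Site | fixed effect | not stated |

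The protocol gives no figure on this point to reproduce.

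**Inputs.** From the protocol: two-sided level 0.05 (6.2.1), three sites (Trial Overview), 88 participants at 44 per arm (6.1), and site-stratified 1:1 blocks of 2 or 4 (2.2). Assumed, because the protocol does not give it: the share R² of lactate variance at one time point that lies between sites.

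**Size for a level at one time point.** With the arms balanced within sites, the true standard error rests on the within-site variance, a fraction 1 − R² of the total. A model without site reports one based on the total. Hence

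- reported SE / true SE = 1/√(1 − R²)
- true type I error = 2 × [1 − Φ(1.96/√(1 − R²))]

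| Assumed R² | SE ratio | Effective critical value | True type I error |
|---|---|---|---|
| 0.02 | 1/√0.98 = 1.010 | 1.96 × 1.010 = 1.980 | 4.8% |
| 0.05 | 1/√0.95 = 1.026 | 1.96 × 1.026 = 2.011 | 4.4% |
| 0.10 | 1/√0.90 = 1.054 | 1.96 × 1.054 = 2.066 | 3.9% |

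**Check by simulation.** One time point; 88 patients in three sites of 44, 22 and 22 (split assumed); site-stratified blocks of 2 or 4; least squares with and without site; 6,000 runs per cell. The effect was set for about 80% power given the within-site variance.

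| Assumed R² | Type I error, site omitted / included | Power, site omitted / included |
|---|---|---|
| 0 | 0.053 / 0.053 | 0.79 / 0.79 |
| 0.02 | 0.046 / 0.049 | 0.77 / 0.78 |
| 0.05 | 0.045 / 0.051 | 0.79 / 0.80 |
| 0.10 | 0.039 / 0.051 | 0.76 / 0.79 |
| 0.20 | 0.030 / 0.051 | 0.72 / 0.79 |

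The Monte Carlo error of a type I error estimate is about √(0.05 × 0.95/6000) = 0.003, so the simulation agrees with the formula. Including site costs nothing visible when sites do not differ, and keeps level and power near their nominal values when they do.

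**Change from 0 h.** Suppose site adds a constant offset to every value of a patient. In the patient's 72 h value minus the 0 h value that offset cancels, together with the patient's own random effect. With complete data, a site main effect then leaves the standard error of this contrast unchanged. The figures above therefore apply to levels and not to change.

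**The case against.** - **Silence is not exclusion.** Section 6.2.3 does not rule site out, and covariates for a supporting biomarker are ordinary content for a separate analysis plan. That is fair, and this may be a drafting slip. But 6.2 is itself headed as the statistical analysis plan and fixes the lactate model down to covariance and imputation; followed as written, it omits the stratification factor.
- **Lactate is not alone.** The Fisher, log-rank and Cox, Wilcoxon, oxygen-consumption and renal biomarker analyses (6.2.4 to 6.2.7) state no site term either, so the text could reflect a rule of adjusting only the primary analysis. This stands as a limit on the point. Lactate is singled out because its model is almost a copy of one that does adjust. The renal biomarkers, also analysed by repeated measures, share the gap.
- **The loss depends on the contrast.** A reader might infer that the lactate standard error is overstated in any case. It is so only if sites differ and the contrast is a level at a time point. The wording on each time point favours levels, but 6.2.3 does not name the contrast.
- **Evidence for site differences is thin.** Section 4.5.2 allows venous or arterial samples, which might suggest differences by site. Nothing shows that the mix differs by site; under 4.5.1 it depends on the patient's access, and a site term would not remove variation within sites.
- **Comparability.** A reader might also infer that the creatinine and lactate results cannot be set side by side. The protocol plans no comparison of the two estimates, so nothing supports that.

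**Conclusion.** The inconsistency is real, and its consequence is small and conservative. If sites account for 2% to 10% of the lactate variance at a time point, the standard error of the difference in levels is about 1% to 5% too large and the true type I error is about 4.8% to 3.9%. In the simulation, power falls by about one point at a share of 2% to 5% and about three points at 10%. The share is an assumption; the protocol offers nothing to narrow it, and at zero there is no effect. The size also assumes near-balance of arms within sites, which the blocks provide.

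Ignoring a stratification factor may suggest bias or too many false positives. Neither follows here: the arms are balanced within sites by design, and the test errs below its nominal level. Lactate is not the primary outcome, is not among the key secondary outcomes in the Trial Overview, 2.1 or 5.1.2, and does not enter the sample size in 6.1. The point is a free improvement and no threat to the trial's main conclusion.

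**What to change.** Add to 6.2.3 the statement already in 6.2.2, that study site enters the model as a fixed effect. Do the same for the repeated-measures analysis of cystatin C, NGAL and KIM-1 in the section on other biomarkers of renal injury (the second one numbered 6.2.7). If leaving site out was intended, say so and give the reason.

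The cost is one sentence in each section and, with three sites, two degrees of freedom per model. No extra data are needed, and the change should be made before unblinding.

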6.2.4 Receipt of Renal Replacement Therapy

Fisher’s exact tests will be used to compare the incidence of renal failure requiring renal replacement therapy during the index ICU stay. This outcome will be truncated at 60 days if the patient remains alive and in the ICU at that time.

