8.1 Risks and Benefits	16
8.1.1 Potential benefits	16
8.1.2 Potential harms	16
9. MONITORING.....	17
9.1 Institutional Review Board (IRB).....	17
9.2 Data Safety and Monitoring Board (DSMB).....	17
10 CLINICAL MONITORING PLAN	17
11. FUNDING	17
12. DATA SHARING	18
References	19

SYNOPSIS

The “The “Thiamine for Renal Protection in Septic Shock (TRPSS)” study is a randomized, clinical trial that aims to determine the impact of Thiamine vs. Placebo on kidney injury in patients with septic shock. The trial will be conducted in accordance with all applicable national and international laws, regulations, and guidelines. The trial and this protocol is developed in accordance with the International Conference on Harmonization (ICH) guidelines¹⁻³ and the Standard Protocol Items: Recommendations for Interventional Trials (SPIRIT) statement^{4,5}. The principal investigator wrote the protocol with input from the steering committee. Any substantial changes or amendments to the protocol will be clearly documented and communicated to all relevant parties.

TRIAL OVERVIEW

Title Thiamine for Renal Protection in Septic Shock (TRPSS)

Clinical Trials Number	NCT03550794
Sources of monetary or material support	National Institute of General Medical Sciences
Study Sites	Beth Israel Deaconess Medical Center, Long Island Jewish Medical Center, North Shore Medical Center
Condition studied	Septic Shock
Interventions	Thiamine 200mg IV twice daily for 3 days
Comparator	Placebo
Inclusion criteria	
1) Adult \geq18 years of age2) Suspected or Confirmed Infection (defined as collection of a blood/fluid culture and provision of an antimicrobial)3) Receipt of a vasopressor agent (e.g. norepinephrine, phenylephrine, vasopressin)4) Serum lactate \geq2mmol/L5) Creatinine $>$1.0mg/dL
Exclusion criteria	
1) Clinical indication for thiamine administration (alcoholism, known or highly suspected deficiency) or treatment with thiamine beyond the amount found in a standard multivitamin within the last 10 days2) Renal replacement therapy within the past 30 days3) Comfort measures only or anticipated withdrawal of support within 24 hours4) Protected populations (pregnant women, prisoners)5) Known thiamine allergy
Study type	Interventional Allocation: Randomized (1:1) Intervention model: Parallel group Masking: Double-blind
Target sample size	88 Participants (44/arm)

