6.2.5 In-hospital mortality

In-hospital mortality will be analyzed using survival analysis. Results will be presented with Kaplan-Meier curves and the groups compared using the log-rank test.⁴⁵ Hazard ratios with 95% confidence intervals will be obtained using Cox’s proportional hazards models.⁴⁶ The proportional hazards assumption will be verified by visual inspection of the Kaplan-Meier curves and statistically by including a product term (i.e. “interaction”) between the treatment group variable and the natural logarithm of time in the model.⁴⁷ If the proportional hazards assumption is not met, only the Kaplan-Meier curves and the p-value from the log-rank test will be presented. The patient will be considered to have survived their hospitalization if they remain alive and in the hospital at 60 days.

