6.2.6 Length of ICU stay

Length of ICU stay will be compared between groups using Wilcoxon Rank Sum tests. As in the above analyses, this will be truncated at 60 days.

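### Site is a randomisation stratum and is in the creatinine model, but the lactate, RRT, mortality and ICU-stay analyses name no site term, which costs some power if sites differ in prognosis

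*Protocol*

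**What the plan says.** Section 2.2 of the protocol states that "Participants will be randomized in a 1:1 ratio to either thiamine or placebo in blocks with random sizes of 2 or 4", and that "The randomization will be stratified according to site". The trial overview names three sites: "Beth Israel Deaconess Medical Center, Long Island Jewish Medical Center, North Shore Medical Center".

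The creatinine analysis follows that design. Section 6.2.2 ends: "Study site will be controlled for as a fixed-effect in the regression model".

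The next four sections do not:

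- **Lactate (6.2.3).** The paragraph closely follows the creatinine paragraph, with the same model, time points and covariance structure, but has no sentence on site.
- **RRT (6.2.4).** Fisher's "exact tests will be used to compare the incidence of renal failure requiring renal replacement therapy during the index ICU stay".
- **In-hospital mortality (6.2.5).** "Results will be presented with Kaplan-Meier curves and the groups compared using the log-rank test". The section adds: "Hazard ratios with 95% confidence intervals will be obtained using Cox", meaning the proportional hazards model. No strata or covariates are named.
- **ICU stay (6.2.6).** "Length of ICU stay will be compared between groups using Wilcoxon Rank Sum tests".

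No reason is given for using site in one analysis only. The synopsis lists RRT, ICU stay and hospital mortality as key secondary outcomes.

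**The concern.** Small permuted blocks within site keep the arms nearly balanced at each hospital, so differences between hospitals largely drop out of the treatment comparison. An unstratified test still counts those differences as random error. If hospitals differ in RRT use, ICU stay, mortality or lactate, the standard error is too large, the true type I error is below the nominal 5%, and some power is given away.

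At stake is efficiency on the secondary outcomes of an 88-patient trial that states no power for them. There is also an inconsistency between the creatinine and lactate models, which are otherwise parallel.

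**Working it through.** **The plan's own figures.** The protocol gives no power, event rate by site or site size for lactate, RRT, mortality or ICU stay, so there is nothing to reproduce. Its one power figure (0.80 at N=80) concerns creatinine and plays no part here.

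**Inputs from the protocol.** 1:1 allocation in blocks of 2 or 4 within site, three sites, 88 patients, two-sided 0.05. **Assumed:** the share R² of outcome variance that site explains, at 2%, 5% and 10%.

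**Step 1: approximation.** With arms balanced within site, the true variance of the treatment difference is (1 − R²) times the variance that an unstratified test uses. Hence:

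- SE ratio = 1/√(1 − R²)
- true alpha = 2 × [1 − Φ(1.96/√(1 − R²))]
- power, where the stratified test has 80%: Φ(2.80 − 1.96/√(1 − R²)), with 2.80 = 1.96 + 0.84

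| R² | SE ratio | Effective critical value | True alpha | Power |
|---|---|---|---|---|
| 0% | 1.000 | 1.960 | 5.0% | 80.0% |
| 2% | 1.010 | 1.980 | 4.8% | 79.4% |
| 5% | 1.026 | 2.011 | 4.4% | 78.5% |
| 10% | 1.054 | 2.066 | 3.9% | 76.9% |

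**Step 2: what such an R² means.** Take RRT with three equal sites and a mean rate of 0.343, so that the total variance is 0.343 × 0.657 = 0.225. Rates of 25/33/45% have a between-site variance of 0.0068, giving R² = 0.0068/0.225 ≈ 3%. Rates of 15/33/55% have 0.0268, giving R² ≈ 12%. The upper end of the range therefore needs very large differences between hospitals.

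**Step 3: simulation.** 8,000 replicates per scenario, N=88, three sites, blocks of 2 or 4 within site. The following are assumptions:

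- site sizes of 60/14/14 and 30/29/29
- moderate site differences: control RRT 25/33/45%, mortality hazard ratios 0.6/1/1.6, log ICU-stay shifts −0.3/0/0.3
- large site differences: 15/33/55%, 0.4/1/2.2, −0.6/0/0.6
- treatment effects for power: RRT odds ratio (3/28)/(11/19) = 0.185, from the counts in Section 1.5; mortality hazard ratio 0.45; log ICU-stay shift −0.6

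Ranges run over the two site-size patterns.

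| Comparison | Site differences | Type I error, planned | Type I error, stratified | Power change, points |
|---|---|---|---|---|
| Fisher vs exact stratified | none | 0.032–0.035 | 0.032–0.039 | +0.1 to +1.6 |
| | moderate | 0.029–0.033 | 0.032–0.039 | +0.7 to +2.0 |
| | large | 0.021–0.028 | 0.030–0.039 | +2.9 to +4.5 |
| Log-rank vs stratified log-rank | none | 0.047–0.051 | 0.047–0.051 | −0.3 to −0.2 |
| | moderate | 0.042–0.045 | 0.051–0.053 | +1.5 to +2.0 |
| | large | 0.031–0.034 | 0.049–0.053 | +5.7 to +6.0 |
| Wilcoxon vs van Elteren | none | 0.051–0.052 | 0.050–0.051 | about −1.1 |
| | moderate | 0.043–0.046 | 0.050–0.055 | +0.6 to +1.1 |
| | large | 0.026–0.036 | 0.051–0.052 | +4.6 to +6.9 |

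The simulation error of a rate near 0.05 is √(0.05 × 0.95/8000) ≈ 0.002, so no planned test exceeds 5% beyond chance. Lactate was not simulated; the reasoning of Step 1 applies to its between-arm comparison at a time point.

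**Step 4: separating Fisher's own conservatism.** With identical sites Fisher's test already runs at 0.032–0.035, so that shortfall is due to discreteness and not to site. The asymptotic Cochran-Mantel-Haenszel test runs at 0.049–0.050 there. In the 60/14/14 case its power is 84.4% against 77.4% for Fisher, but an unstratified Pearson chi-square test reaches 85.0%. The gain of 7 points comes from leaving the exact test, not from stratifying.

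**The case against.** The sponsor could fairly answer as follows.

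- **Nothing is invalid.** This stands. False positives are not increased, and the primary outcome, which alone determines the sample size, already adjusts for site.
- **The loss is hypothetical and small.** This largely stands. The protocol contains no evidence that the hospitals differ. With no or moderate differences the power change is about −1 to +2 points, and only large assumed differences give about 3 to 7.
- **Simple tests are reasonable with 88 patients and possibly small strata.** This stands in part. A site with few patients or no events adds little to a stratified test, but with only three strata the cost of stratifying is about 1 point at worst.
- **Strata can be left to an analysis plan.** This has some force for the log-rank and Cox analyses, where Section 6.2.5 is silent. It has less for Fisher's and the Wilcoxon tests, which are named outright, and for lactate, where the site sentence of the parallel model is absent. Section 6.2 is itself headed as the statistical analysis plan.

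A reader might also infer that Fisher's test shows how much is lost by ignoring site, because full enumeration at exactly 44 per arm gives a true alpha of 1.9% to 2.9% for RRT rates of 10% to 30%. That inference fails. The figure reflects discreteness: at 43 v 45 it becomes 3.0% to 3.9%. Exactly 44 v 44 analysed is not assured either, given blocks within three sites and an analysis limited to dosed participants. An exact stratified test would keep most of this conservatism.

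**Conclusion.** The point holds as a minor matter of efficiency and consistency. Site is a design stratum and a covariate for creatinine, yet the lactate, RRT, mortality and ICU-stay analyses name no site term and no reason is given. The planned analyses stay valid and are conservative only as far as sites differ in prognosis. For an assumed site R² of 2% to 10%, true alpha is about 4.8% to 3.9% and the loss from 80% power is about 0.6 to 3.1 points. With identical sites there is no loss.

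A reader might conclude that these tests are conservative whatever the sites look like. The protocol does not support that, since it reports neither site-specific outcomes nor site sizes. The result rests on the assumed R² range and on near balance of the arms within site. It does not touch the conclusion on creatinine.

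**What to change.** Revise Sections 6.2.3 to 6.2.6 so that each analysis uses the randomisation strata:

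- **Lactate:** add study site as a fixed effect, as in the creatinine model.
- **RRT:** a site-stratified Cochran-Mantel-Haenszel test with a stratified risk difference and its 95% confidence interval. Use the exact version only if the data are sparse, noting that it keeps the conservatism due to discreteness.
- **In-hospital mortality:** site-stratified log-rank test and Cox model. The section on other renal biomarkers (the second numbered 6.2.7) also lists hospital mortality under t-tests and chi-square tests, and should be reconciled at the same time.
- **ICU stay:** the van Elteren test, that is, the Wilcoxon test stratified by site.

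If the sponsor prefers the simple tests, a sentence saying why site is used only for creatinine would settle the inconsistency.

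The cost is wording only, with no new data. A site with no events or very few patients will contribute little, and up to about 1 power point may be lost if the sites turn out alike.

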6.2.5 In-hospital mortality

In-hospital mortality will be analyzed using survival analysis. Results will be presented with Kaplan-Meier curves and the groups compared using the log-rank test.⁴⁵ Hazard ratios with 95% confidence intervals will be obtained using Cox’s proportional hazards models.⁴⁶ The proportional hazards assumption will be verified by visual inspection of the Kaplan-Meier curves and statistically by including a product term (i.e. “interaction”) between the treatment group variable and the natural logarithm of time in the model.⁴⁷ If the proportional hazards assumption is not met, only the Kaplan-Meier curves and the p-value from the log-rank test will be presented. The patient will be considered to have survived their hospitalization if they remain alive and in the hospital at 60 days.

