2. TRIAL DESIGN

2.1 Overview

This will be an investigator-initiated, randomized, placebo-controlled, parallel group, double-blind, superiority trial of thiamine vs. placebo in participants with septic shock. A total of 88 adult participants will be enrolled. The primary outcome will be the change serum creatinine between enrollment and 72-hours. Key secondary outcomes include the incidence of renal failure during the index ICU stay and survival at 30 days.

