4.4.1 Contingencies and Participant Withdrawal

- In the unlikely event that a participant is discharged alive from the hospital prior to 3 days after enrollment, all study medications will be stopped. The participant will remain in the study and will be followed for outcomes.
- If a patient is transferred to the hospital ward from the intensive care unit, the study drug will continue while the patient is in the hospital until 3 days.
- If the clinical team decides to give the participant vitamin B1 for clinical purposes, the study drug will be continued (including thiamine) as long as the total maximum dose of vitamin B1 is $\leq 1,500\text{mg/day}$. 1,500mg day is a standard dose for Wernicke's encephalopathy at many institutions and has not been associated with any increased harm.
- If a participant withdraws from the study, further administration of study meds will be stopped. Data collected prior to withdrawal will be maintained and the patient will be followed for outcomes, but additional data will not be collected.

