5.1.2 Key Secondary Outcomes

- Incidence of Acute Renal Failure
- Length of ICU stay
- In-hospital Mortality
- Other biomarkers of renal injury (Serum cystatin C, NGAL, and KIM-1)
- Peripheral blood mononuclear cell mitochondrial oxygen consumption

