7. DATA COLLECTION AND MANAGEMENT

7.1 Data collection process

Data collection will be the responsibility of the principal investigator. Creatinine and lactate levels will be obtained from blood draws at 0hr, 24hr, 48hr, and 72hr. Most other variables (i.e. demographics, sepsis characteristics and laboratory results) will be obtained prospectively from the electronic medical record up until the time the patient dies or is discharged from the hospital. Data will be entered directly into the online database software (see below).

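### Section 6.2.5 sets Kaplan-Meier, log-rank and Cox for in-hospital mortality but does not say how patients discharged alive before day 60 are handled; ordinary censoring at discharge would overstate mortality

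*Protocol*

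**What the plan says.** Section 5.1.2 lists "In-hospital Mortality" among the key secondary outcomes. Section 6.2.5 fixes the analysis: "In-hospital mortality will be analyzed using survival analysis". It continues: "Results will be presented with Kaplan-Meier curves and the groups compared using the log-rank test". It adds: "Hazard ratios with 95% confidence intervals will be obtained using" Cox models, with a check of proportional hazards. Its one rule on survivors reads: "The patient will be considered to have survived their hospitalization if they remain alive and in the hospital at 60 days".

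Three other places bear on the point.

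- **Section 7.1** says that most variables other than creatinine and lactate are taken from the medical record "up until the time the patient dies or is discharged from the hospital".
- **Section 4.4.1** says of a participant discharged before day 3: "The participant will remain in the study and will be followed for outcomes". Section 2.1 names "survival at 30 days" as a key secondary outcome. Neither describes how vital status after discharge would be obtained, and section 6.2 has no analysis of 30-day survival.
- **The paragraph of section 6.2 on other biomarkers of renal injury** also lists hospital mortality, among outcomes to be compared by t-test or chi-square test.

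**The concern.** A survival analysis needs a rule for when each patient leaves the risk set. Section 6.2.5 gives one for patients still in hospital at day 60 and none for those discharged alive earlier, who are likely to be most of the survivors. If discharge is their last observation, standard practice with the named methods censors them there.

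For this endpoint, live discharge is not loss of information: the patient has survived the hospital stay. Censoring at discharge treats such patients as if they still faced the inpatients' risk of dying in hospital. The Kaplan-Meier curve then estimates mortality in a setting where nobody is discharged, which is higher than the proportion who die in hospital. The log-rank test and hazard ratio compare the daily death rate among patients still in hospital. A treatment that shortens the stay could lower in-hospital mortality with a hazard ratio of 1. One that speeds or slows death and discharge equally could move the hazard ratio with almost no change in deaths.

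The two readings of section 6.2.5 can therefore give different curves, hazard ratios and p-values from the same data.

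**Working it through.** The protocol states no event rate, hazard ratio or power for in-hospital mortality, so there is no figure of its own to reproduce. From the documents come the methods, the 60-day limit, 44 patients per arm (6.1) and the two-sided 0.05 level (6.2.1). Section 1.1 gives background mortality above 40% but does not call it in-hospital. The 40% below and all times and hazards are assumptions.

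**Step 1: the curve.** Let a proportion p = 0.40 die in hospital, with exponential time to death of mean d. The rest are discharged alive at a lognormal time with median c and log-scale SD 0.7. With S_D and S_L the survivor functions of the two times and f_D the density of time to death, the death hazard among inpatients is

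h(t) = p·f_D(t) / [p·S_D(t) + (1−p)·S_L(t)].

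With discharge censored, Kaplan-Meier mortality at day 60 is 1 − exp(−∫h), integrated from 0 to 60. True in-hospital mortality is p·(1 − exp(−60/d)), which is 40.0% in every row.

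| Mean time to death d | Median time to discharge c | Kaplan-Meier, discharge censored |
|---|---|---|
| 5 days | 20 days | 43.6% |
| 8 days | 20 days | 50.0% |
| 5 days | 12 days | 51.4% |
| 8 days | 12 days | 68.2% |

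**Step 2: other inputs.** Take constant daily hazards, λ for death and μ for live discharge, with mean stay L = 1/(λ+μ). True mortality by day 60 is λ/(λ+μ) × (1 − exp(−60(λ+μ))); the discharge-censored curve gives 1 − exp(−60λ). For true 40% and L = 10, λ = 0.40/(1 − exp(−6))/10 = 0.0401, and the curve reaches 1 − exp(−2.406) = 91%. In the same way, with mean stays of 10, 14 and 20 days:

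- true 20% gives 70%, 58% and 47%;
- true 30% gives 84%, 73% and 61%;
- true 40% gives 91%, 82% and 72%.

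The size depends heavily on the inputs; the direction does not.

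**Step 3: the hazard ratio.** Same formulas.

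- Death hazard 0.04 in both arms, discharge hazard 0.06 against 0.09: true mortality is 39.9% against 30.8%, and the hazard ratio is 1.00.
- Both hazards multiplied by 0.75, to (0.03, 0.045): true mortality is 39.9% against 39.6%, and the hazard ratio is 0.75.

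**Step 4: the log-rank test.** Simulated trials with 44 patients per arm, two-sided 0.05, showing the share of trials that reject.

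| Death and discharge hazards, arm 1 / arm 2 | True mortality | Discharge censored | Kept to day 60 |
|---|---|---|---|
| (0.03, 0.04) / (0.03, 0.04) | 42% / 42% | about 5% | about 5% |
| (0.03, 0.04) / (0.03, 0.08) | 42% / 27% | about 5% | about 27% |
| (0.03, 0.04) / (0.045, 0.06) | 42% / 43% | about 23% | about 6% |

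In the first row treatment affects neither rate, and both versions hold their level. They part only when treatment changes the rate of discharge.

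**The case against.** The strongest reply is that censoring at discharge is written nowhere. The 60-day sentence may name only the doubtful group because a patient discharged alive has plainly survived. On that reading discharged patients are event-free to day 60, and the analysis is sound. A reader might infer that the protocol prescribes censoring at discharge and that its curve and hazard ratio are therefore wrong; the text does not support that. What stands is that no sentence chooses between the readings, and the usual one for these methods gives the biased curve.

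A reader might also infer that all follow-up stops at discharge. Section 7.1 covers most other variables and does not expressly include vital status, and sections 2.1 and 4.4.1 point to some later follow-up. This does not remove the gap, because neither gives a procedure and a death after discharge is not an in-hospital death.

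Nor is a discharge-censored hazard ratio invalid. It is a proper cause-specific hazard ratio for death while in hospital, and its test keeps its level when treatment affects neither rate. It answers a different question from the risk of dying in hospital.

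A censoring date is often left to a separate plan. Here, though, the protocol's own analysis section fixes the methods, the proportional-hazards check and half of the survivor rule.

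Finally, a chi-square comparison of proportions, as in the biomarker paragraph, would not be affected by censoring. But nothing says which analysis is the main one, so it adds a conflict rather than a safeguard.

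**Conclusion.** The point holds as an unresolved rule with a material effect. If live discharges are censored at discharge, the Kaplan-Meier curve overstates in-hospital mortality: about 44% to 68% at day 60 against an assumed true 40% over the times in step 1, and more under the inputs in step 2. The test and hazard ratio would describe the death rate among inpatients. These can miss a difference in in-hospital deaths, or suggest one where there is almost none, if treatment changes time to discharge. Section 6.2 also gives two incompatible analyses of the same outcome.

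The sizes rest on assumed times and hazards, since the documents give none. The outcome is secondary in a trial sized for creatinine, so the primary conclusion is not touched. The change is worth making because it is nearly free and alters what would be published.

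**What to change.** Add to section 6.2.5: *Patients discharged alive before day 60 are counted as event-free and stay in the risk set to day 60; they are censored at day 60, not at discharge.* The curve then ends at the observed proportion dead in hospital by day 60, and the log-rank test and hazard ratio refer to the stated endpoint.

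Reconcile the biomarker paragraph of section 6.2 with section 6.2.5 by naming one main analysis of hospital mortality and removing the other or labelling it supportive.

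The cost is a few words and a changed censoring date in the analysis data set; no new data are needed. The hazard ratio must then be described as one for in-hospital death over 60 days, not as a daily death rate among inpatients. Deaths after discharge remain uncounted, so earlier discharge alone can lower the measured mortality. That is a limit of the endpoint itself, and the report should say so.
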